13.1.3. Appendix C Screening Form

Screening

Please answer the following questions to the best of your abilities.

- 1. Are you at least 18 years old? (DOB?)
- 2. Do you suffer from symptoms of indigestion and/or heartburn (see severity index below)? (Y/N)
- 3. Have you ever been diagnosed with any chronic liver disease? (Y/N)
- 4. Have you ever been diagnosed with any chronic renal disease? (Y/N)
- 5. Are you pregnant or breastfeeding? (Y/N)
- 6. Do you have any allergies to any of the following? (Y/N)
 - a. Licorice
 - b. Artichoke leaf
 - c. Marshmallow Root
 - d. Ginger
 - e. Chamomile
 - f. Rice Hull Concentrate
 - g. Carrageenan
 - h. Cellulose Capsule
- 7. Do you have more than 10 alcoholic beverages per week? (Y/N)
- 8. Are you willing to try the test product for relief of your indigestion and heartburn symptoms? $(\frac{Y}{N})$
- Have you been prescribed any medication by your doctor for any GI disorder or medication that can affect the GI system? (Y/N)
- 10. Have you ever had surgery of the upper GI tract or abdominal surgery (with the exception of having your gallbladder or appendix removed)? (Y/N)
- 11. Are you currently taking any anticoagulation, blood-thinning, medication daily (aspirin, warfarin, etc.)? (Y/N)
- 12. Are you able to swallow pills? (Y/N)

Severity index

Dyspepsia: Dyspepsia Symptom Severity Index (DSSI)

Aims

To develop a self-report measure to quantify the severity of dyspepsia symptoms in clinical practice and research.

Dyspepsia symptom severity index (DSSI) Scale/item Dysmotility-like 1. Frequent burping or belching 4. Bloating 5. Feeling full after meals 6. Inability to finish normal-sized meals 7. Abdominal (belly) discomfort, without pain, after meals 8. Abdominal (belly) distension (feels as though you need to loosen your clothes) 12. Nausea before meals 13. Nausea after meals 14. Nausea when you wake up in the morning 15. Retching (heaving as if to vomit, with little result) 16. Vomiting Reflux-like 3. Burping with bitter tasting fluid in throat 17. Regurgitation of bitter fluid into your mouth (reflux) during the 18. Regurgitation (reflux) at night 19. Burning feeling in your chest (heartburn) 20. Burning feeling in your stomach 9. Abdominal (belly) ache or pain right after meals 10. Abdominal (belly) pain before meals or when hungry 11. Abdominal (belly) pain at night Overall item


Comments

This is a self-administered questionnaire of 20 items. The numbers in the table state the following order of the items in the questionnaire. The grading of the items by the patient should be on a 0 (absent) to 4 (very severe) Likert scale. One global item is included in order to gather data on the patient's overall impression of his/her dyspepsia symptom severity.

A total score is represented by the mean across the three subscales (dysmotility-, reflux-, and ulcer-like symptoms).

References

13.1.4. Appendix D Baseline Form

Baseline

 Demograph 	ics
-------------------------------	-----

- a. Race/Ethnicity (Black or African American, White, Asian, American Indian or Alaska Native, Native Hawaiian or another pacific islander, other: _____, do not want to share)
- b. Sex (M, F, or Do not want to share)
- 2. On average how often do you get Indigestion and Heartburn? (few times a year, once a month, A few times a month, once a week, 2-3 times a week, Everyday)
- 3. How long does it usually take for your symptoms to reach maximum intensity? (0-30 min, 31 min- 1 hour, +1 hour)
- 4. How long do your symptoms usually last without medication? (0-30 min, 31 min- 1 hour,, 1-2 hour, >2 hours, do not resolve)
- 5. How long do your symptoms usually last with medication? (0-30 min, 31 min- 1 hour,, 1- 2 hour, >2 hours, Do not resolve)
- 6. On average how bad are your symptoms without medication? (1-10)
- 7. On average how bad are your symptoms with medication? (1-10)
- 8. What symptoms do you experience when you are having an episode of Heartburn/Indigestion? (Check all that apply)
 - a. bloating
 - b. early fullness during a meal
 - c. pain or discomfort in the upper abdomen
 - d. burning in the upper abdomen
 - e. pain/burning in the center of your chest
 - f. nausea
 - g. vomiting
 - h. burping
 - i. other:
 - j. None of the above
- Do any of the following bring on or trigger your symptoms of indigestion or heartburn? (Check All That Apply)
 - a. Overeating
 - b. Eating too quickly
 - c. Fatty/greasy foods
 - d. Spicy foods
 - e. Caffeine
 - f. Alcohol
 - g. Smoking
 - h. Other:
 - i. None of the above

- 10. Do you take medications to treat your symptoms? (yes/no)
 - a. What medication do you take? (free response)
 - b. how long do you wait before taking medication?
 - i. Right away
 - ii. Within an hour
 - iii. 1-2 hours
 - iv. >2 hours

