4.4. Data Collection

All data in the present study will be self-reported by the participant and collected via their online portal (Hawthorne Effect Study Visit Management System (HE VMS)). Participants will be asked to take the test product according to the instructions for use, complete study surveys and respond to study reminders during the course of the study. The instructions for use and study forms can be found in the appendix. (*Appendices B, D, E, F, G*)

5. Study Population

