6.1. Study Procedures

- Candidates will review information about the study and complete a screening form.
- During the screening process, the candidate will be asked questions regarding their symptoms and medical history to ensure that they meet the requirements to participate in this study.
 Potential participants will also be asked questions to ensure that they do not meet any of the exclusion criteria and meet all of the inclusion criteria.
- After successful screening (participant does not meet any exclusion criteria), participants will review and sign study informed consent form.
- Upon verification of signed informed consent, participant will be enrolled into the study.
- At time of enrollment, participant will be given access to the HIPAA compliant study portal.
 - The study portal provides access to study information, signed informed consent form, instructions for test product use, frequently asked questions, study surveys, symptom diary, and data collection tools.
- Participant shall complete baseline assessments upon access to the portal.
 - Baseline assessment will include questions regarding the participants' demographics, medications, detailed information regarding their indigestion/heartburn including treatment.
- To ensure that baseline assessments are completed before test product is used by the
 participant, study materials and study welcome package will be shipped to the participant once
 the clinical study manager/clinical ops coordinator confirms that the baseline assessment has
 been completed.
- The welcome package will include an information sheet that will outline instructions for their participation in the trial, the test product, and paper forms of the documents (paper form of

- study documents will be provided for real time data collection, in the event that the participant cannot log into the study portal to input data).
- Once the participant receives the test product, the participant will log into the study portal to acknowledge the receipt of the test product.
- Study start date will be the reported date of receipt of test product.
- Participant will be sent weekly email reminders that remind them of their participation in the study.
- At the onset of the indigestion and heartburn episode, the participant will start a Symptom Diary and complete a 4-point Likert scale for each of the symptoms they are experiencing.
 - Onset is defined as the point in time the participant takes the test product for relief of symptoms.

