- After completing the surveys, the participant will take the test product. The participant will take
 2 capsules per indigestion and heartburn episode. With a max of 6 capsules per day. (If
 participant takes 6 capsules in 1 day this will be defined as 3 indigestion and heartburn episodes
 and the participant will be exited from the study).
- After taking the test product, the participant will complete a 4-point Likert scale assessment for each symptom at 15 minutes, 30 minutes, and 1 hour after taking the test product.
- When the participants symptoms have resolved , the participant will complete the symptom diary.
- If the participant takes any other medication outside of the test product, the participant will record this on the symptom diary.
 - The participant is allowed to take alternative medications or supplements AFTER 1 hour from taking the test product.
- After taking the test product, the participant will be instructed to fill out an Adverse Event form for any side-effects experienced.
- After the first episode of indigestion and heartburn, the participant will be asked to complete the same process for another 2 episodes within the 60-day study time frame; however, these are not required.
- If the participant completes the required assessments for a total of 3 episodes of indigestion and heartburn, they will be prompted, by email, to exit the study.
- If the participant only completes the required assessments for the required 1 episode of indigestion and heartburn, the participant will be prompted, by email, to complete the study exit form and will be exited from the study on day 60 (60 days from the day of receipt of the test product).
- Neither the sponsor nor Hawthorne Effect Inc. will not collect any unused test product.
- Upon receipt of study exit survey and review of completed study forms, participant will receive an Amazon gift card of \$25 via email.

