6.2. Study Schedule of Activities

Assessments	Screening	Consent	Before Receipt of Test Product	Test Product Received	Event 1	15 Minutes After Event Start	30 Minutes After Event Start	60 Minutes After Event Start
Study Window								
Screening Survey	X							
Consent		X						
Baseline Survey			X					
Demographics			X					
Acknowledgement of receipt of test product				X				
Symptom Diary					X			X
4-point Likert Scale					X	X	X	X
Test Product Consumed					X			
Medications & Supplements			X					
AE Assessment					X	X	X	X
Study Exit Survey								

Assessments	Event 2	15 Minutes After Event Start	30 Minutes After Event Start	60 Minutes After Event Start	Event 3	15 Minutes After Event Start	30 Minutes After Event Start	60 Minutes After Event Start	Study Exit
Study Window									
Screening Survey									
Consent									
Baseline Survey									
Demographics									
Acknowledgement of Receipt of Test Product									
Symptom Diary	X			X	X			X	
4-point Likert Scale	X	X	X	X	X	X	X	X	
Test Product Consumed	X				X				
Medications & Supplements									
AE Assessment	X	X	X	X	X	X	X	X	X
Study Exit Survey									X

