7.3. Analysis Plan

Separate tables will be presented showing the changes from baseline for each component and each time point. The changes will be evaluated by the paired sample t-test. A longitudinal analysis will be performed for participants who report on more than one incident of heartburn or indigestion.

General statistical methods:

Data will be analyzed using standard statistical methods, as further specified in a statistical analysis plan (SAP), which will be prepared in detail later.

- Data analysis will largely consist of summary statistics and graphs. The only formal group comparisons will be in covariate analyses.
- For continuous variables data presentation will consist of means, confidence intervals computed using the *t*-statistic, medians, and interquartile ranges. Group comparisons will use *t*-tests or ANOVA.
- For discrete variables confidence intervals will use the exact intervals, where available. Group comparisons will use Fisher's exact test, with the Monte Carlo version used where computationally necessary.
- For time to event variables analysis will use the Kaplan-Meier algorithm, and group comparisons will use the log-rank or proportional hazards methods, depending on the data type.
- Visual analog scale values will be treated as continuous variables. Frequency counts will also be provided for scales with 10 or fewer distinct response levels.
- Covariate analyses will investigate the relation between baseline and outcome variables, using methods appropriate to the data types involved. Age, gender, and baseline medications will be included in these analyses where appropriate data are available.
- Present intention is that the analysis will be performed in R, and the precise form of algorithms will be the default of R. Kaplan-Meier, log-rank, and proportional hazards algorithms will be the defaults of the survival package.

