Severity = Moderate • Occurrence = Possible • Level of Evidence = **D**

Animal research suggests that marshmallow can have hypoglycemic effects (62022). Theoretically, marshmallow might have additive effects with hypoglycemic therapy (4). Monitor blood glucose levels closely. Dose adjustments to antidiabetes drugs may be necessary. Some antidiabetes drugs include glimepiride (Amaryl), glyburide (DiaBeta, Glynase PresTab, Micronase), insulin, pioglitazone (Actos), rosiglitazone (Avandia), and others.

LITHIUM

Interaction Rating = Moderate Be cautious with this combination.

Severity = Moderate • Occurrence = Probable • Level of Evidence = **D**

Marshmallow is thought to have diuretic properties. Theoretically, due to these potential diuretic effects, marshmallow might reduce excretion and increase levels of lithium. The dose of lithium might need to be decreased.

ORAL DRUGS

Interaction Rating = **Moderate** Be cautious with this combination.

Severity = Moderate • Occurrence = Possible • Level of Evidence = **D**

The mucilage in marshmallow might impair absorption of oral drugs (1,11,12,19).

Interactions with Herbs & Supplements

ANTICOAGULANT/ANTIPLATELET HERBS AND SUPPLEMENTS: Animal research suggests that marshmallow flower extract has antiplatelet effects (92846). Theoretically, concomitant use of marshmallow with herbs and supplements with anticoagulant/antiplatelet effects might increase the risk of bleeding in some people. These herbs include angelica, clove, danshen, garlic, ginger, ginkgo, Panax ginseng, red clover, turmeric, willow, and others.

HERBS AND SUPPLEMENTS WITH HYPOGLYCEMIC POTENTIAL: Animal research suggests that marshmallow may have hypoglycemic effects (62022). Theoretically, marshmallow might have additive effects when used with other herbs and supplements with hypoglycemic potential. This might increase the risk of hypoglycemia in some patients. Some herbs and supplements with hypoglycemic potential include alpha-lipoic acid, bitter melon, chromium, devil's claw, fenugreek, garlic, guar gum, horse chestnut, Panax ginseng, psyllium, Siberian ginseng, and others.

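### Sections 6.1, 6.2 and 2.2.2 provide for a general medication and supplement history before product receipt, but visible Appendix D item 10 asks only about medicines taken for the symptoms

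*Combined protocol and SAP*

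**What the plan says.** Section 6.1 says the baseline assessment will cover "demographics, medications, detailed information regarding their indigestion/heartburn including treatment", so medications are listed separately from treatment of the indigestion. The schedule in 6.2 has its own row, "Medications & Supplements", marked once, in the column before receipt of test product. Section 2.2.2 lists documentation of routine medicines and supplements among the potential benefits. Section 7.3 adds, for the covariate analyses: "Age, gender, and baseline medications will be included in these analyses where appropriate data are available".

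The visible Appendix D has ten items. Item 10 asks "Do you take medications to treat your symptoms", followed by a free-text drug name and how long the participant waits before taking it. Items 4 to 7 ask how long and how bad symptoms are with and without medication, but do not ask which medicines are used. Supplements are not mentioned.

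Section 4.4 states "All data in the present study will be self-reported by the participant and collected via their online portal" and places the study forms in the appendices. Under 6.1, product ships once "the clinical study manager/clinical ops coordinator confirms that the baseline assessment has" been completed.

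**The concern.** A form that asks only about symptom medicines cannot produce the history that 6.1 and 6.2 schedule. Two things depend on that history.

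The first is the 7.3 covariate. With item 10 alone, baseline medications would mean heartburn and indigestion remedies. The two yes/no drug questions at screening add almost nothing, because a yes disqualifies and the answers are then nearly constant among those enrolled.

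The second is the use of the sponsor's own interaction list. For marshmallow and lithium, Appendix A rates occurrence as probable and says "The dose of lithium might need to be decreased". For marshmallow and antidiabetes drugs it advises close glucose monitoring and possible dose adjustment. The trial can follow up such advice only for participants it knows to be taking these drugs.

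**Working it through.** The check is mainly a comparison of the plan with each visible form.

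| Source | What it asks or does about medicines | When |
|---|---|---|
| Appendix C item 9 | Yes/no: prescription for a GI disorder, or one that can affect the GI system | Screening |
| Appendix C item 11 | Yes/no: daily blood thinner | Screening |
| Appendix D item 10 | Medicines taken for the symptoms | Before shipment |
| Appendix E (diary) | Other medicines taken for the episode | After dosing |
| Appendix F | Whether the product avoided alternative medication | Exit |
| Appendix G | Adverse event details; no medication list | After dosing |

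No row gives a list of current medicines and supplements before the first dose. The diary instruction in 6.1 ("If the participant takes any other medication outside of the test product") applies only once the product has been taken.

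**Could another step catch these users?** Eligibility is decided automatically by the screening questionnaire (5.2). Good health is defined there by the conditions the questionnaire asks about, which are chronic liver and chronic renal disease; diabetes and psychiatric illness are not among them. The pre-shipment step in 6.1 confirms that the baseline is complete, with no stated reading of the answers. The only stated review of completed forms comes at exit, before the gift card.

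**Appendix A, counted by hand.**
- Rated drug entries: licorice (DGL) 8 + artichoke 0 + ginger 8 + chamomile 10 + marshmallow 4 = 30.
- Entries for warfarin or other anticoagulant/antiplatelet drugs, the class in screening item 11: 1 (DGL) + 3 (ginger) + 1 (chamomile) + 1 (marshmallow) = 6. The remainder is 30 - 6 = 24.
- Entries advising cautious use or avoidance for an enzyme's substrates: DGL with CYP2B6, and chamomile with CYP1A2, 2C9, 2D6 and 3A4 = 5.
- Entries with occurrence rated probable: 2, namely licorice with warfarin (screened) and marshmallow with lithium (not named on any visible form).
- Entries that mention changing the dose of the participant's own drug: 2, marshmallow with lithium and marshmallow with antidiabetes drugs.

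**Exposure.** 2 capsules per episode x 3 episodes = 6 capsules (6.1 and 6.6).

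**Sample size.** Section 7.2 gives a mean improvement of 0.5, SD 1.5 and 97 participants for 90% power. With d = 0.5/1.5 = 0.333 and two-sided alpha 0.05 (assumed, since the section does not state it), the noncentral t gives power 0.901 at n = 97 and 0.898 at n = 96, so 97 is reproduced. No medication variable enters that calculation or the paired t-test, so neither changes.

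**The case against.** The strongest objection is that the appendices do not show every portal form. Section 4.3 mentions a start form for product receipt, and 7.1 a general-health questionnaire given at baseline and exit; neither appears in a visible appendix. The medications row in 6.2 is separate from the baseline survey row, so it too could be a portal form that is not reproduced. This stands, and it limits the finding to the visible forms. It does not show that such a form exists. A separate row does not settle the matter either, since demographics also has its own row and sits inside Appendix D.

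Existing questions also cover more than the count of 24 suggests. Prescribed proton pump inhibitors, listed under CYP2C19, fall under screening item 9, and their use for symptoms falls under item 10. Both CYP2C9 entries include warfarin. A previous cancer diagnosis is an exclusion in 5.2, which would remove many tamoxifen users, although the screening form does not ask about cancer. Item 9 might catch other users too, but it names no drug and leaves the judgement to the participant.

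A reader might infer that nobody can act on Appendix A before the first dose. The documents do not support that. The consent text and the product insert (Appendix H) are not visible and may carry a warning, and candidates can put questions to the investigator at consent. What can be said is that no visible form identifies these users to the trial.

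A reader might also infer that the 7.3 analysis relies on these data. It does not: the sentence is conditional on data being available, and 7.1 describes the secondary analyses as hypothesis generating.

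**Conclusion.** The mismatch holds for the visible forms, with medium confidence. Sections 6.1 and 6.2 schedule a history that Appendix D, used as written, would not collect. The effects are a 7.3 covariate confined to symptom medicines and no identification, before shipment, of participants taking lithium or antidiabetes drugs.

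The importance is low. It would be wrong to read this as a demonstrated safety hazard: 2.2.1 calls the interactions theoretical, the marshmallow entries for lithium and antidiabetes drugs are evidence level D, exposure is at most six capsules, and the one entry rated as not to be taken together (licorice with warfarin) is already screened. The documents give no figure for how many participants use these drugs, so the number affected cannot be estimated. The primary analysis and the sample size are not touched.

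The conclusion assumes that the portal questions match the appendices and that no unseen form collects the history.

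**What to change.** Reword Appendix D item 10 to: *List all medicines and supplements you currently take, for any reason*, and keep the present symptom-medicine question as a sub-item. If another portal form already collects this, the sponsor need only identify it and add it to the appendices. The cost is one longer form item.

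Optionally, at the existing pre-shipment confirmation in 6.1, the coordinator could flag lithium or glucose-lowering drugs to the investigator, who would advise the participant. Starting with these two is a practical choice, because they are the entries that mention a dose change. Flagging every enzyme substrate would bring in common drugs such as ibuprofen and losartan. The load is one brief list check per participant: 200 at the initial target, 1.25 x 200 = 250 at the 125% limit in 5.1, and more if the target is recomputed upward. If 1% to 10% of 200 used such drugs (an assumption), 2 to 20 people would be flagged.

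No new exclusion criterion is needed for advice alone. Any decision not to ship would need a stated criterion, because participants are enrolled at consent: someone never sent product would count toward the 200 but could not enter the ITT population, which requires at least one dose.

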13.1.5. Appendix E Symptom Diary

Please complete the following items during your first episode of Indigestion/Heartburn. We encourage you to complete the forms online in real time. However, if you cannot log into your patient portal at the time of your symptoms please complete these forms and log into your patient portal as soon as possible and complete the online forms.

Reminder: Do not take any other medications or supplements within the first hour of taking the test product.

Date of Onset:	Ti	me of Onset:	
Trigger (check all that apply Food □ Caffeine □ Alcol □ Smoking □Other:	nol		
Time test product taken:			
Please rate the followin answer.	g symptoms at th	e following time point	s. Circle one
Onset (Prior to Bloating 0 No Symptom		2	3
No Symptom	Slight	Moderate	Severe

Early Fullness During a 1	Meal	2	3			
No Symptom	Slight	Moderate	Severe			
Pain or Discomfort in the	e Upper Abdomen	2	3			
No Symptom	Slight	Moderate	Severe			
Burning in the Upper Ab		2	2			
0 No Symptom	1 Slight	2 Moderate	3 Severe			
Pain/Burning in the center	er of your chest					
0 No Symptom	l Slight	2 Moderate	3 Severe			
J 1	S					
Nausea						
0 No Symptom	1 Slight	2 Moderate	3 Severe			
1 to Symptom	Siigiit	Woderate	Severe			
Vomiting						
0 No Symmton		2 Madamata	3			
No Symptom	Slight	Moderate	Severe			
Burping						
0	1	2	3			
No Symptom	Slight	Moderate	Severe			
Other						
0	1	2	3			
No Symptom	Slight	Moderate	Severe			
15 Minutes after taking the test product						
Bloating						
0	1 Slight	2 Moderate	3 Sayara			
No Symptom	Slight	Moderate	Severe			

Early Fullness During a Meal 0 1 2 3							
No Symptom	Slight						
Pain or Discomfort in the	Upper Abdomen	_	_				
0	I C1: 14	2	3				
No Symptom	Slight	Moderate	Severe				
Burning in the Upper Abo	lomen						
0	1	2	3				
No Symptom	Slight	Moderate	Severe				
Pain/Rurning in the center	r of vour chost						
Pain/Burning in the cente	1	2	3				
No Symptom	Slight	Moderate	Severe				
- · · · · · · · · · · · · · · · · · · ·	38		20100				
Nausea							
0	1	2	3				
No Symptom	Slight	Moderate	Severe				
Vomiting		_	•				
0	l C1: 14	2	3				
No Symptom	Slight	Moderate	Severe				
Burping							
0	1	2	3				
No Symptom	Slight	Moderate	Severe				
Other:							
0	1	2	3				
No Symptom	Slight	Moderate	Severe				
30 Minutes after taking the test product							
Bloating							
0	1	2	3				
No Symptom	Slight	Moderate	Severe				

Early Fullness During a M	Meal		3		
0 No Symptom	2				
Dain or Discomfort in the	Unner Abdemen				
Pain or Discomfort in the	Opper Abdomen	2	3		
No Symptom	Slight	Moderate	Severe		
Burning in the Upper Ab	domen				
0 No Symptom	1 Slight	2 Moderate	3 Severe		
Pain/Burning in the center	er of your chest				
0	1	2	3		
No Symptom	Slight	Moderate	Severe		
Nausea					
0	1	2	3		
No Symptom	Slight	Moderate	Severe		
Vomiting					
0	1	2	3		
No Symptom	Slight	Moderate	Severe		
Burping					
0	1	2	3		
No Symptom	Slight	Moderate	Severe		
Other:	1	2	3		
0 No Symptom	Slight	Moderate			
No Symptom	Stight	Woderate	Severe		
60 Minutes afte	er taking the	e test product			
Bloating					
0	1	2	3		
No Symptom	Slight	Moderate	Severe		

Early Fullness During a Meal 0 No Symptom	1 Slight	2 Moderate	3 Severe		
Pain or Discomfort in the Upp 0 No Symptom	oer Abdomen 1 Slight	2 Moderate	3 Severe		
Burning in the Upper Abdom 0 No Symptom	en 1 Slight	2 Moderate	3 Severe		
Pain/Burning in the center of 0 No Symptom	your chest 1 Slight	2 Moderate	3 Severe		
Nausea 0 No Symptom	1 Slight	2 Moderate	3 Severe		
Vomiting 0 No Symptom	1 Slight	2 Moderate	3 Severe		
Burping 0 No Symptom	1 Slight	2 Moderate	3 Severe		
Other: 0 No Symptom	1 Slight	2 Moderate	3 Severe		
After your symptoms resolveplease complete any of the following questions if applicable.					
Did your symptoms resolve completely with the test product? Yes No Time of complete symptom resolution:					

Did you need to take another medication	on: Yes N	No
Medication #1:	Dose:	Time:
Medication #2:	Dose:	Time:
Medication #3:	Dose:	Time:
Did your symptoms resolve completely	with taking your altern	native medication? Yes No
After taking the alternative medication,	, time of complete resol	lution of symptoms:

Did you experience any side effects after taking the test product? (Y/N) If yes, **Please fill out** the Adverse Event form.

